2.4.4 Analyses of efficacy endpoints

2.4.4.1 Analysis of primary efficacy endpoint(s)

2.4.4.1.1 Annualized rate of severe exacerbation events during the 52-week placebo-controlled treatment period

Primary statistical model (ITT analysis) and adjustment for covariates

The primary analysis of the annualized rate of severe exacerbation events during the 52-week placebo-controlled treatment period is to assess the efficacy of dupilumab in an intention-to-treat setting. In this primary approach, off-treatment measurements of patients who prematurely discontinue treatment will be included for the analysis. Patients who permanently discontinue the study medication will be encouraged to return to the clinic for all remaining study visits. If a patient stays in study until the end of 52-week treatment period, all severe exacerbation events that happen up to Visit 18 will be included in the primary analysis, regardless if the patient is on treatment or not. And the observation duration is defined as from randomization to Visit 18. If a patient withdraws from study prior to the end of 52-week treatment period, all observed severe exacerbation events up to the last contact date will be included in the analysis, and the observation duration is defined as from randomization to the last contact date. No imputation will be performed for the unobserved events that may happen after study discontinuation and up to Week 52. This estimand compares the rate of severe exacerbation for the patients randomized to the dupilumab and placebo arms, regardless of what treatment patients actually received. It assesses the benefits of the treatment policy or strategy relative to placebo (7).

The annualized rate of severe exacerbation events will be analyzed using a negative binomial regression model. The model will include the total number of events occurring during the observation period defined above as the response variable, with the four treatment groups, age, region (pooled country), baseline eosinophil strata, baseline ICS dose level and number of severe exacerbation events within 1 year prior to the study as covariates. Treatment groups, region, baseline eosinophil strata and baseline ICS dose level will be treated as categorical variable. Age and number of severe exacerbation events within 1 year prior to the study will be treated as continuous variable. Severe asthma exacerbation event prior to the study is defined as treatment with a systemic steroid (oral or parenteral) for worsening asthma at least once or hospitalization or emergency medical care visit for worsening asthma (as defined in section [Section 2.1.1](#)). Log transformed observation duration will be the offset variable.

Pairwise comparisons of the annualized event rates between each dose of dupilumab and its matching placebo will be derived by testing each dupilumab group versus its matching placebo separately. The estimated annualized event rate for each treatment group and its two-sided 95% confidence intervals will be derived from the negative binomial model. The event rate ratio of each dupilumab group and its matching placebo, two-sided 95% confidence interval of the rate ratio based on the negative binomial model and its p-value will be provided.

Based on EMEA feedback, the rate difference between each dupilumab group and its matching placebo, two-sided 95% confidence intervals of the rate difference and its p-value derived using delta method will also be provided as supportive information.

Sample SAS code can be found below:

```
proc glimmix data=event;  
  class eosblgpn ics trt01pn cntygrln;  
  model numevents=trt01pn age eosblgpn ics cntygrln asmanum  
    /offset=logdur dist=negbin link=log solution;  
run;
```

If the model fails to achieve convergence, different estimation algorithms will be applied following the order: default→LAPLACE→QUAD(8). If the issue still exists, other handling may be considered. The adjustment will be added to the footnote of the corresponding outputs.

The gross estimated of annualized events rate will also be presented by each treatment group. Mean cumulative function plot will be provided for descriptive purpose.

Estimand of clinical efficacy of dupilumab versus placebo

An analysis to assess the efficacy of dupilumab if patients adhere to the treatment as directed is also specified. In this approach, off-treatment measurements of patients who prematurely discontinue treatment will be excluded from the analysis. A negative binomial model with the same set of covariates as specified in the primary analysis will be used. This model will include severe exacerbation events occurring during the treatment epoch as the response variable and the log transformed duration of the treatment epoch will be the offset variable. This approach defines the estimand to be the efficacy of dupilumab with treatment adherence (7).

Handling of missing data

If patients withdraw from the study before Visit 18 (Week 52), severe exacerbation events that may occur after study discontinuation will not be observed. These patients are considered as patients with missing data on severe exacerbation. Number of patients with missing data, reasons and timing for patient withdrawals will be summarized by treatment groups. Summary statistics of selected demographic and baseline disease characteristics will be provided for patients with missing data and patients with complete data separately. Graphical summaries of the dropout patterns such as Kaplan-Meier plots of time to study discontinuation with different reasons of discontinuation may be provided to examine if there is any different missing pattern between treatment groups. In addition, following sensitivity analyses will be conducted to assess the robustness of the conclusion of the main model

- *Pattern mixture model - multiple imputation (PMM-MI)*

For each patient with missing data of severe exacerbation events, individual monthly event probability will be estimated using observed data with adjustment of the planned treatment

group, age, region (pooled country), baseline eosinophil strata, baseline ICS dose level, and number of severe exacerbation events within 1 year prior to the study. And binary event will be imputed on monthly basis using multiple imputation.

- *Control-based PMM-MI*

For each patient with missing data of severe exacerbation events, individual monthly event probability will be estimated using observation in the matching placebo arms only, with adjustment of age, region (pooled country), baseline eosinophil strata, baseline ICS dose level, and number of severe exacerbation events within 1 year prior to the study. And binary event will be imputed on monthly basis using multiple imputation.

- *Tipping point analysis*

For each patient with missing data of severe exacerbation events, the monthly event will be imputed in a similar fashion as PMM-MI based on various odds values. If the patient is on dupilumab, the predicted odds will be increased; if the patient is on Placebo, the predicted odds value will be decreased. The adjusted rate will then be used to impute the number of events that would occur during the missing observation period. A sequence of increasing/decreasing ratio will be used to generate different imputed datasets.

For each of the above methods, a negative binomial model will be fitted using each of the complete datasets composed of observed and imputed data, including the total number of observed and imputed events during the 52 weeks as the response variable, with the treatment group, age, region (pooled country), baseline eosinophil strata, baseline ICS dose level and number of severe exacerbation events within 1 year prior to the study as covariates. Log transformed observation duration will be the offset variable for patients who complete the 52-Week treatment/study period, and log transformed 52 weeks will be the offset variable for patients who discontinue the study before Visit 18 (Week 52). SAS MIANALYZE procedure will be used to generate statistical inferences by combining results from the analysis with each dataset using Rubin's formula.

More details of the imputation and analyses methods are provided in [Appendix D](#).

Subgroup analyses

To assess consistency of treatment effects across the subgroup levels, subgroup analyses will be performed for the annualized rate of severe exacerbation event during the 52-week treatment period by:

- Age group: < 18, 18-64, ≥ 65 years; < 18, ≥ 18 years
- Gender (Male, Female)
- Region (Asia: Japan, South Korea and Taiwan; Latin America: Argentina, Brazil, Colombia, Chile and Mexico; East Europe: Hungary, Poland, Russia, Turkey and Ukraine; Western Countries: Australia, Canada, France, Germany, Italy, South Africa, Spain, United Kingdom and USA)

- Territory (North America: Canada and USA; European Union: France, Germany, Hungary, Italy, Poland, Spain and United Kingdom; Rest of World: Argentina, Australia, Brazil, Colombia, Chile, Japan, Mexico, Russia, South Africa, South Korea, Taiwan, Turkey and Ukraine)
- Race (Caucasian/White, Black/of African descent, Asian/Oriental, all the other)
- Ethnicity (Hispanic, non-Hispanic)
- Baseline blood eosinophil level (≥ 0.3 Giga/L, <0.3 Giga/L; ≥ 0.15 Giga/L, < 0.15 Giga/L)
- Background ICS dose levels at randomization (medium, high)
- Background controller type at randomization (ICS and LABA only, ICS and LABA and Anti-leukotrienes only, Other; ICS, LABA and any third controller, Other)
- Baseline FEV1 (≤ 1.75 , > 1.75 L)
- ACQ-5 (≤ 2 , >2)
- Number of severe asthma exacerbation prior to the study as defined in [Section 2.1.1](#) (1, >1)
- Baseline weight (< 70 , $\geq 70 - < 90$, ≥ 90 kg; <60 , ≥ 60 kg)
- Baseline BMI (< 25 , $25- <30$, ≥ 30 kg/m²)
- Smoking history (Former, Never)
- Atopic medical condition (Yes, No)
- Age of onset of asthma (<18 , $18-40$, >40 years)
- Baseline predicted FEV1% ($<60\%$, $60\%-90\%$)
- Baseline periostin(NG/ML) ($< \text{median}$, $\geq \text{median}$)
- Baseline fractional exhaled nitric oxide (FeNO) (< 25 , $\geq 25- < 50$, ≥ 50 ppb)

Treatment by subgroup interaction and its p-value will be derived from a negative binomial model. This model will include the total number of events occurring during the observation period as the response variable, with the four treatment groups, age, region (pooled country), baseline eosinophil strata, baseline ICS dose level, number of severe exacerbation events within 1 year prior to the study, subgroup (if different than the aforementioned covariates) and treatment by subgroup interaction as covariates. Log transformed observation duration will be the offset variable. If quantitative treatment by subgroup interaction is detected with nominal p-value < 0.05 for any subgroup factor, the Gail-Simon test will be performed to evaluate possible qualitative interaction. Summary statistics of severe exacerbations will be provided within each subgroup. Forest plot of relative risks and corresponding CIs and forest plot of risk differences and corresponding CIs comparing each dupilumab dose group vs. its matching placebo for the subgroups will be provided.

For local submission, efficacy analyses may be performed in specific countries/regions, eg, Japan.

Loading dose evaluation (Sustained treatment effect evaluation)

To examine if the loading dose has any confounding effect on annualized rate of severe exacerbation during the 52-week randomized treatment period, a sensitivity analysis for the annualized rate of severe asthma exacerbation will be performed. It will include severe exacerbation events occurring after the first four weeks and 12 weeks, respectively, and only on-treatment events will be included to avoid possible confounding effect due to off-treatment data. Due to potential insufficient number of events after excluding data from the first 12 week, two dupilumab groups will be combined and two placebo groups will be combined. Results of the sensitivity analysis will be compared to the result of on-treatment analysis including all on-treatment severe exacerbation events during the study.

2.4.4.1.2 Absolute change from baseline in pre-bronchodilator (pre-BD) FEV₁ at Week 12

Primary statistical model (ITT analysis) and adjustment for covariates

The primary analysis of change from baseline in pre-BD FEV₁ at Week 12 is to assess the efficacy of dupilumab in a real-world setting. The absolute change from baseline in FEV₁ at Week 12 will be analyzed using a mixed-effect model with repeated measures (MMRM) approach. The model will include change from baseline in pre-BD FEV₁ values up to Week 12 as response variables, and treatment, age, sex, baseline height, region (pooled country), baseline eosinophil strata, baseline ICS dose level, visit, treatment by-visit interaction, baseline pre-BD FEV₁ value and baseline-by-visit interaction as covariates. Treatment groups, sex, region, baseline eosinophil strata, baseline ICS dose level, and visit will be treated as categorical variables. Age and height will be treated as continuous variable. For patients who discontinue the treatment before Week 12, they will be asked and encouraged to return to the clinic for all remaining study visit and the additional off study-treatment pre-BD FEV₁ values measured up to Week 12 will be included in the primary analysis. For patients who withdraw from the study before Week 12, pre-BD FEV₁ values will be missing after study discontinuation. No imputation will be performed for missing values in the primary analysis. This estimand compares the change from baseline in pre-BD FEV₁ for the patients randomized to the dupilumab and placebo arms, regardless of what treatment patients actually received. It assesses the benefits of the treatment policy or strategy relative to placebo (7).

An unstructured correlation matrix will be used to model the within-patient errors. Parameters will be estimated using restricted maximum likelihood method with the Newton-Raphson algorithm. Statistical inferences on treatment comparisons for the change from baseline in pre-BD FEV₁ at Week 12 will be derived from the mixed-effect model. Difference in LS mean change from baseline, the corresponding 95% CI and the p-value with Kenward-Roger adjustment will be provided for comparison for each dupilumab group against its matching placebo. In addition, descriptive statistics including number of patients, mean, standard error and LS mean of change from baseline will be provided.

A sample SAS code can be found below:

```
proc mixed data=adsd.adre method=reml;
  where paramcd='FEV1' and avisitn ge 3 and avisitn le 8 and ittfl='Y';
  class subjid sex eosblgpn ics trt01pn avisitn cntygrln;
  model chg = trt01pn sex age height ics eosblgpn cntygrln avisitn
trt01p*avisitn base base*avisitn/ddfm=kr residual;
  repeated avisitn/type=un subject=subjid;
  lsmeans trt01pn*avisitn /pdiff cl ;
  estimate '300 mg q2w vs Placebo 2ml q2w at Week 12 Visit 8'
trt01pn 0 -1 0 1 trt01pn*avisitn 0 0 0 0
0 0 0 -1
0 0 0 0
0 0 0 1/ cl;
run;
```

If MMRM model fails to achieve convergence due to complexity of model specification, we may add some procedures to handle this issue including: 1) using maximum likelihood estimation instead of restricted maximum likelihood method; 2) covariance structure selection to reduce the number of unknown parameters to be estimated, the path is UN→TOEPH→TOEP→AR(1)→CS. The adjustment will be added to the footnote of the corresponding outputs.

Estimand of clinical efficacy of dupilumab versus placebo

To assess the treatment effect when the patients adhere to the study treatment as directed, on-treatment pre-BD FEV1 measurements will be analyzed using the similar MMRM model as for the primary analyses, including same set of covariates and estimation algorithm. The model will include on-treatment change from baseline in pre-BD FEV1 values up to Visit 8 (Week 12) as response variables. A pre-BD FEV1 value is considered as on-treatment if it's measured before or on the last dose date + 14 days.

Sensitivity analyses with different censoring methods for pre-BD FEV1 potentially confounded by systemic corticosteroid use

In addition, two sets of sensitivity analyses with different methods of handling pre-BD FEV1 measurements confounded by the systemic corticosteroid use will be performed:

- Censoring method 1: pre-BD FEV1 measurements collected from systemic corticosteroid start date to systemic corticosteroid end date + 14 days will be excluded in order to reduce the confounding effect of systemic corticosteroids
- Censoring method 2: All pre-BD FEV1 measurements collected on and after first day of systemic corticosteroid use will be excluded.

The above two censoring methods will be applied to both primary analyses and on-treatment analysis. On-treatment analysis with data censoring method 1 will be used to provide treatment effect size estimates without confounding effect of systemic corticosteroid use.

Handling of missing data

If a patient misses scheduled pre-BD FEV1 measurement during the first 12-week treatment, or withdraws from the study before Visit 8 (Week 12), he/she will have missing pre-BD FEV1 data at some time points up to Week 12. Descriptive statistics of pre-BD FEV1 by visit up to Week 12 will be summarized for patients with some missing data and patients with complete data up to Week 12 separately. Number of patients with missing pre-BD FEV1, reasons and timing for missing pre-BD FEV1 will be summarized by treatment groups. In addition, following sensitivity analyses will be conducted to assess the robustness of the conclusion of the main model:

- *Pattern mixture model-multiple imputation (PMM-MI)*

Missing pre-BD FEV1 values will be imputed multiple times with adjustment for covariates including treatment groups, baseline eosinophil groups, age, sex, height, region, baseline ICS dose level and reason of treatment discontinuation. Each of the complete datasets will be analyzed using the ANCOVA model with change from baseline in pre-BD FEV1 at Week 12 as the response variable, treatment, age, sex, height, region (pooled country), baseline eosinophil strata, baseline ICS dose level, and baseline pre-BD FEV1 value as covariates. Then the SAS MIANALYZE procedure will be used to generate statistical inference by combining results using Rubin's formula.

- *Control based PMM-MI*

The analysis is similar as the standard PMM-MI described above, except that it assumes that after withdrawal from the study, patients from the dupilumab groups would exhibit the same future evolution of pre-BD FEV1 as patients on the placebo who were not exposed to dupilumab.

- *Tipping point analysis*

First, missing values will be imputed by PMM-MI as illustrated above. The imputed values in placebo group will then be shifted by adding a sequence of positive values and the imputed values in dupilumab group will be shifted by subtracting a sequence of positive values. For each combination of the shift parameters, each of the imputed and shifted datasets will be analyzed with the ANCOVA model and their results will be combined using Rubin's formula to generate statistical inference. LS mean difference between dupilumab and placebo in change from baseline in pre-BD FEV1 at week 12 and the corresponding p-values will be provided for each combination of shift parameters.

More details of the imputation and analyses methods are included in [Appendix D](#).

Subgroup analysis

To assess the consistency treatment effects across the subgroup levels, subgroup analyses will be conducted for the change from baseline in pre-BD FEV1 at Week 12 with the same set of subgroups as defined for the annualized rate of severe exacerbation events. Treatment-by-subgroup interaction at Week 12 and its p-value will be derived from a MMRM model. The model will include change from baseline in pre-BD FEV1 values up to Week 12 as response variables,

and treatment, age, sex, height, region (pooled country), baseline eosinophil strata, baseline ICS dose level, visit, treatment by-visit interaction, baseline pre-BD FEV1 value, baseline-by-visit interaction, subgroup (if different than the aforementioned covariates), subgroup-by-treatment interaction and subgroup-by-treatment-by-visit interaction as covariates. If quantitative treatment by subgroup interaction at Week 12 is detected with nominal p-value < 0.05 for any subgroup factor, the Gail-Simon test will be used to test the qualitative interaction. Summary statistics of change from baseline in pre-bronchodilator FEV1 will be provided within each subgroup. Forest plot of LS mean difference and corresponding CIs comparing each dupilumab dose group vs. its matching placebo for the subgroups will be provided.

Distribution of change from baseline in pre-BD FEV1

Cumulative distribution function of change from baseline in pre-BD FEV1 at Week 12 and Week 52 will be presented.

For each subgroup, a MMRM model will be used to analyze change from baseline in pre-BD FEV1 at Week 12. Change from baseline in pre-BD FEV1 up to Week 12 will be included as response variable. Treatment groups, age, sex, height, region (pooled country), baseline eosinophil strata, baseline ICS dose level, visit, treatment by-visit interaction, baseline pre-BD FEV1 value and baseline-by-visit interaction will be included as covariates. LS mean change from baseline in pre-BD FEV1 at Week 12 for each treatment group and LS mean difference in change from baseline in pre-BD FEV1 at Week 12 for each dupilumab treatment group compared to placebo will be derived from the MMRM model for each subgroup.

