#### **11.4.2.4 Loading dose evaluation**

To examine if inclusion of the loading dose may impact demonstration sustained efficacy regard to exacerbations, additional sensitivity analyses of the annualized rate of severe exacerbation will be performed by excluding severe exacerbation events occurring during the first four weeks and 12 weeks, respectively. The analyses will be performed the same way as the primary analysis. To avoid possible confounding effect due to off-treatment data, only on-treatment events will be included. Due to potential insufficient number of events after excluding data from the first 12 weeks, two dupilumab groups will be combined and two placebo groups will be combined.

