1.6 STATISTICAL MODIFICATIONS MADE IN THE STATISTICAL ANALYSIS PLAN

This section summarizes major changes in statistical analysis features made in approved SAP versions from statistical considerations in protocol or previous SAP versions, with emphasis on changes after study start (after the first patient was enrolled). These changes are made before database lock.

The statistical analysis plan history table below gives the timing, rationale, and key details for major changes to the statistical analysis features in the statistical analysis plan.

Table 2 - Statistical analysis plan statistical changes

SAP version number	Date approved	Rationale	Description of statistical changes
1	24-Jun-2016	Expand the multiplicity control procedure for additional secondary endpoints, sub-populations.	The testing order of secondary endpoints was expanded from protocol, and the complete list of endpoints to be tested in the hierarchical order was specified in Table 6
1	24-Jun-2016	To be aligned with protocol amendment 07	Anti-dupilumab antibody (ADA) status (negative or titer value, if positive in the ADA assay) at Visit 2 (Day 1), Week 12, Week 24, Week 52 and follow up at Week 64 will be provided.
1	24-Jun-2016	To meet the request from FDA to assess any potential confounding effects of the loading dose on efficacy.	Sensitivity analyses were added to examine if the treatment effect of dupilumab is sustained throughout the 52-week treatment period or if there is any confounding effect of the use of the loading dose resulting in a larger treatment effect in the early part of the study. Annualized rates of severe exacerbation will also be analyzed versus placebo excluding efficacy data obtained during the first 4 weeks and 12 weeks of treatment of dupilumab/placebo respectively.

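### The loading-dose evaluation compares a late-period rate ratio with a full-period one that contains the same events, so it is a weak check for a larger early effect; early-period rate ratios should be added

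*SAP*

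**What the plan says.** SAP 1.6 (Table 2) records that these analyses were added at a regulator's request about possible confounding of efficacy by the loading dose. It names two things to examine: whether the effect lasts through 52 weeks, and whether there is "any confounding effect of the use of the loading dose resulting in a larger treatment effect in the early part of the study". Protocol 11.4.2.4 frames the purpose as sustained efficacy: "additional sensitivity analyses of the annualized rate of severe exacerbation will be performed by excluding severe exacerbation events occurring during the first four weeks" and, separately, the first 12 weeks.

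SAP 2.4.4.1.1, under its loading-dose heading, gives the analysis set: "It will include severe exacerbation events occurring after the first four weeks and 12 weeks, respectively, and only on-treatment events will be included". Because few events may remain after the 12-week exclusion, "two dupilumab groups will be combined and two placebo groups will be combined". The only comparison described is this: "Results of the sensitivity analysis will be compared to the result of on-treatment analysis including all on-treatment severe exacerbation events during the study".

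The comparator is the adherence estimand earlier in the same section: "This model will include severe exacerbation events occurring during the treatment epoch as the response variable". It takes its covariates from the primary model, which has four treatment groups.

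Neither document plans an early-period rate ratio, a treatment-by-period term, a confidence interval for the late-minus-full difference, or a rule for judging agreement. The offset for the truncated period is not stated either.

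**The concern.** The comparison sets a part against the whole. Events after Week 4 or Week 12 enter both rate ratios, and only the full-period figure also holds the early events, which come from 4 or 12 of 52 weeks. A strong early effect therefore moves the full-period figure only a little. The two estimates are also highly correlated, so laying their separate confidence intervals side by side says little about whether they differ.

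At stake is how the second question in SAP 1.6 is answered. A report could present two similar rate ratios as evidence against a larger early effect when the comparison had little ability to reveal one.

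**Working it through.** **Inputs** (SAP 1.3 and 1.4): placebo rate 0.6 per year, dispersion 2, rate ratio (RR) 0.27/0.6 = 0.45, 546 patients per dupilumab dose and 273 per placebo group, 52 weeks, two-sided 5%. Pooled as in the loading-dose section, this is 1092 against 546. The documents give no early or late RR, so those below are assumptions.

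**The plan's own figure.** The documents state no power for this evaluation, so I checked the inputs against the exacerbation power. The variance of log RR is (1/0.27 + 2)/546 + (1/0.6 + 2)/273 = 0.01045 + 0.01343 = 0.02388, so SE = 0.1545. Then |ln 0.45|/SE - 1.96 = 0.7985/0.1545 - 1.96 = 3.21, a power of 99.9% (stated 99%). For the eosinophil subgroup (230 and 115), SE = 0.238 and power is 91.8% (stated 91%). The inputs reproduce.

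**Dilution.** With constant placebo risk and equal exposure, and w the early share of follow-up:

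RR_full = w × RR_early + (1 - w) × RR_late

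RR_late/RR_full = 1 / [1 - w(1 - RR_early/RR_late)], which is at most 1/(1 - w) when the early effect is the stronger one.

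| | Week 4 cut | Week 12 cut |
|---|---|---|
| w | 4/52 = 0.077 | 12/52 = 0.231 |
| Cap, 1/(1 - w) | 1.083 | 1.300 |
| RR_full if RR_early = 0.20, RR_late = 0.45 | 0.431 | 0.392 |
| RR_late/RR_full in that case | 1.045 | 1.147 |
| RR_full if RR_early = 0, RR_late = 0.45 | 0.415 | 0.346 |

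An early RR of 0.20 against a late RR of 0.45 is a 2.25-fold difference. The planned comparison would show it as 0.43 vs 0.45 or 0.39 vs 0.45. If the early share of placebo events were anywhere from 4% to 30%, the cap would run from 1.04 to 1.43.

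**Reading the two intervals side by side.** I used gamma-Poisson simulation, 2000 trials per scenario, with no dropout and no covariates. With early RR 0.20 and late RR 0.45, the full-period RR lay inside the late RR's 95% CI in at least 99.5% of trials, for either cut, pooled or by single dose. The two log RRs correlate at about 0.98 (Week 4) and 0.93-0.96 (Week 12). In the pooled Week 12 case their SEs are 0.118 and 0.111. Treated as independent, the SE of their difference would be √(0.118² + 0.111²) = 0.162, but the actual paired SE is 0.038.

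**What the same data can show.** In that scenario a direct early-versus-late contrast, pooled, has power of about 55-61% at Week 4 and 94-96% at Week 12 across independent simulations. It rejects in about 5% of trials when there is no early excess. At early RR 0.30 the power falls to about 21% and 50%.

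**Sustained effect.** If early RR is 0.20 and late RR is 1.0, the late estimate centres on 1.00 and its upper 95% limit falls below 1 in only about 2% of trials. The late RR does that job by itself.

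**The case against.** The best defence is that late versus full is the natural comparison for the question the loading-dose section itself poses, namely whether the loading dose distorts the 52-week rate. On that reading the small caps are the answer: early events cannot move the 52-week estimate far. This stands, and it is why the planned comparison should be kept. It does not cover the further clause in SAP 1.6 about a larger early effect.

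A reader might go further and infer that an early excess cannot show at all. The documents and the arithmetic do not support that. At Week 12 the two figures can differ by 30%. With a pooled early RR of 0.10, the full-period RR falls outside the late CI in about 17% of simulated trials. A paired late-minus-full test would recover about as much as a direct contrast (pooled power 0.64 at Week 4 and 0.96 at Week 12 for early RR 0.20). The information is present; the plan lacks an interval that uses it. High agreement rates also depend on an assumed criterion, because the SAP sets none.

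Other outputs bear on timing. SAP 2.4.4.1.1 says "Mean cumulative function plot will be provided for descriptive purpose", and SAP 2.4.4.2.3 plans Kaplan-Meier curves and event probabilities from Week 12. These are useful, but the plot sits with the ITT analysis and the Kaplan-Meier results cover first events only, on or off treatment. Neither gives an early-period rate ratio or an early-versus-late contrast.

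Finally, the remedy has limits. Power is low for a moderate excess. Exclusions E 04 and E 06 (recent exacerbation or respiratory infection) may make Week 0-4 events fewer than projected. Both dupilumab regimens include a loading dose, so no early/late contrast can separate it from time on treatment. All of this stands, and it belongs in the report.

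**Conclusion.** The concern holds as a cheap improvement. The planned comparison shrinks an early excess to at most 1.08-fold (Week 4) or 1.30-fold (Week 12) and comes with no paired interval, so it is a weak check of the second question in SAP 1.6. The caps assume roughly constant placebo risk and equal exposure; the illustrative gaps and powers also rest on assumed early and late RRs.

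It would be wrong to infer that the evaluation is empty or that the regulator's request is unmet. The late-period RR answers the sustained-effect question, and late versus full shows the influence of early events on the 52-week result. The analysis lies outside the testing hierarchy in SAP 2.4.4.3, so no primary or secondary conclusion changes.

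**What to change.** In SAP 2.4.4.1.1, keep the late-period analysis and its comparison with the full period, and add:

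- On-treatment rate ratios for Weeks 0-4 and Weeks 0-12, each beside the corresponding later-period rate ratio.
- The early/late ratio of rate ratios with its 95% CI, from one model per cut: treatment, period, treatment-by-period, log exposure within each period as offset, and standard errors clustered by patient.
- The same pooling of arms for the early, late and full-period figures, and a stated offset for the truncated period.
- A sentence saying that the contrast describes early versus late effect and does not by itself attribute a difference to the loading dose.

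The cost is SAP wording and one model per cut, with no new data. The intervals will be wide. Under the plan's rates, Weeks 0-4 hold about 0.6 × 546 × 4/52 = 25 placebo and 0.27 × 1092 × 4/52 = 23 dupilumab events. With no early excess, the SE of the log early/late ratio is then about 0.31, so the 95% limits lie a factor of about exp(1.96 × 0.31) = 1.8 either side of the estimate. At Week 12 the SE is about 0.19 and the factor about 1.5. A non-significant contrast should therefore be reported with its interval and not read as absence of a moderate early excess.
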